4.4.1 Primary Efficacy Endpoint

4.4.1.1 Primary Efficacy Endpoint Definition

The primary endpoints for this study are the change from baseline in the mean Total MLSI (A×I) at Week 8 within each study product.

[figure not shown]
Extrinsic dental stain will be assessed on the facial surfaces of the 6 maxillary and 6 mandibular anterior teeth (6-11 and 22-27), and the lingual surfaces of the 6 mandibular anterior teeth (22-27) at baseline, Week 4, and Week 8 (Visits 2-4) using MLSI.

The facial and lingual surfaces of each assessable tooth will be divided into 2 regions, with a total of 4 sites per tooth surface (Figure 4-2).

- **Gingival Region:** Defined as a crescent-shaped band (~ 2 mm wide) adjacent to the free margin of the gingiva and extending to the crest of the inter-dental papillae of the adjacent teeth (1 site).

- **Body Region:** The remainder of the tooth surface (the body) is further sub-divided into 3 sites.
 - Distal facial, body facial, mesial facial sites
 - Distal lingual, body lingual, mesial lingual sites

Figure 4-2 MLSI Assessment Sites: Body (B), Gingival (G), Mesial (M), Distal (D)

Area (A) and intensity (I) of extrinsic dental stain is scored separately for the four 'gingival' and 'body' sites, as follows.

Score	Area	Intensity
0	No stain	No stain
1	Stain covering up to one third of region	Light stain
2	Stain covering up to two thirds of region	Moderate stain
3	Stain covering more than two thirds of region	Heavy stain

The mean Total MLSI ($A \times I$) score for each subject at each visit is calculated as the mean of all MLSI ($A \times I$) scores over all non-missing gingival, body, mesial and distal sites on the facial surfaces of the six maxillary anterior teeth and six mandibular anterior teeth, and the lingual surfaces of the six mandibular anterior teeth.

Descriptive statistics (n, mean, SD, SE, median, minimum, and maximum) will be presented for the mean Total MLSI at each time point (absolute and change from baseline) in Table 14.2.2.1.1 for all subjects in mITT population by study product. Raw means (\pm SE) of the mean Total MLSI scores at each time point will be plotted by study product in Figure 14.2.1.1 for all subjects in mITT population.

Individual and derived MLSI ($A \times I$) score data will be listed for each subject by visit and study product group in Listing 16.2.6.1.1 and Listing 16.2.6.1.2 respectively for all randomized subjects.

4.4.1.2 Statistical Hypothesis, Model, and Method of Analysis

The following null and alternative hypotheses will be evaluated:

- H_0 : There is no difference between baseline and week 8
- H_1 : There is a difference between baseline and week 8

The following study product comparisons will be analyzed:

- For Experimental Dentifrice 1, baseline versus week 8

- For Experimental Dentifrice 2, baseline versus week 8

The change from baseline in the mean Total MLSI (A×I) score will be analysed using a Mixed Model with Repeated Measures (MMRM). Fixed effects will be included for smoking status, study product, visit and study product x visit interaction. The baseline mean Total MLSI (A×I) score will be included as a covariate. Subject will be included as a repeated measure with unstructured covariance matrix. Kenward Rogers degrees of freedom approach will be applied. The least square means for each study product at week 8 will be presented based on observed margins and used to test for a non-zero change from baseline. If unstructured covariance matrix does not converge, compound symmetry covariance matrix will be used.

Using the above model, the adjusted mean change from baseline in the mean Total MLSI (A × I) score will be reported by study product group along with 95% confidence intervals (CIs) and adjusted p-values testing for a non-zero change from baseline will be provided in Table 14.2.2.1. For each Experimental Dentifrice, only adjusted p-values following the graphical approach (see [Figure 4-1](#)) will be presented. Significance testing will be conducted at the two-sided 5% significance level.

The assumption of normality and homogeneity of variance in the MMRM will be investigated. In case of violation of these assumptions, a suitable nonparametric test (the Van Elteren test, adjusted for the randomization stratification) will be performed for each comparison at week 8 and results will be provided to support the MMRM results.

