2.2 Background

Both experimental dentifrices contain 5% KNO_3 and 0.2542% sodium fluoride (NaF). The efficacy of KNO_3 -containing dentifrices for the relief of DH ([Schiff et al., 1994](#), [Gillam, 1996](#)) and the anti-caries benefit associated with use of topical NaF ([Featherstone, 1999](#), [Marinho et al., 2003](#)) are well-established.

The sponsor has completed four clinical studies evaluating the dental cleaning properties of dentifrices containing 1% alumina and 5% STP.

- Clinical study CCI ██████████ evaluated the ability of 4 experimental dentifrices (including a 1% alumina and 5% STP dentifrice) to lighten tooth color (whiten teeth) compared to a regular fluoride dentifrice (Aquafresh Advanced), after 4 weeks twice daily brushing. A statistically significant improvement in tooth shade (1.48 units, VITA Classic shade guide), versus baseline, was observed for the 1% alumina and 5% STP dentifrice; there was no statistically significant difference between any of the test products and the regular fluoride dentifrice.
- Clinical study CCI ██████████ evaluated the stain removal efficacy of 4 experimental dentifrices (including a 1% alumina and 5% STP dentifrice), compared to a regular fluoride dentifrice (Aquafresh Advanced), after 8 weeks twice daily brushing. The 1% alumina and 5% STP formulation demonstrated statistically significantly better stain removal (as measured by MLSI) versus the regular fluoride dentifrice after 8 weeks use.
- Clinical study CCI ██████████ found that 8 weeks' twice daily brushing with 2 experimental dentifrice formulations, both containing 1% alumina and 5% STP, provided a statistically significant reduction of dental stain (as measured by MLSI) from baseline; no statistically significant differences were observed between the test products and a regular fluoride dentifrice.
- Clinical study CCI ██████████ evaluated the stain prevention properties of an experimental dentifrice containing 1% alumina and 5% STP formulation. The study demonstrated statistically significantly less stain build-up (as measured by MLSI) after 8 weeks twice-daily use, compared to a regular fluoride dentifrice.

In all the above clinical studies, study treatments were found to be generally well tolerated.

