Exploratory	
To evaluate and compare the change in tooth color co-ordinates after 4 and 8 weeks twice daily use of either a '5% KNO ₃ /1% alumina/5% STP' dentifrice or a '5% KNO ₃ /1% alumina/ 5% STP/2% silica' dentifrice, compared to a regular fluoride dentifrice, as measured using the VITA EasyShade.	Change from baseline in mean tooth shade, L*, a*, b*, WI _D and ΔE* determined using the VITA EasyShade instrument at weeks 4 & 8
Safety	
To assess the safety and tolerability of the two experimental KNO ₃ dentifrices.	Treatment emergent adverse events

Mean MLSI values calculated for the facial surfaces of the six maxillary anterior teeth and six mandibular anterior teeth, and the lingual surfaces of the six mandibular anterior teeth.

Mean tooth shade/color values are calculated for the facial surfaces of the 4 central and lateral maxillary incisors.

This study will be considered successful if either of the experimental dentifrices demonstrates statistically significant stain removal (as measured by mean Total MLSI (Area x Intensity) from baseline after 8 weeks twice daily use).

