1.4 Sample Size Calculation

The study will be powered sufficiently (>90%) to provide evidence of superiority for an Experimental Dentifrice compared to the Reference Dentifrice for both stain removal and whitening after 8 weeks under the graphical approach method (with initial two-sided alpha allocation of 5% for testing within each Experimental Dentifrice) to adjust for multiple comparisons and preserve a two-sided 10% family wise error rate as described in Figure 4-1.

Table 1-4 Sample Size Power by Endpoint at 5% and 2.5% Significance Levels with 90 Subjects per Arm

Endpoint at Week 8	Assumptions		Independent power from 90 subjects per arm for each endpoint by two-sided significance level ³		Power from graphical approach to achieve statistical significance at 5% level ⁴
	Mean Difference	Standard Deviation (SD)	5%	2.5%	
Within Experimental Dentifrice change from baseline in mean Total MLSI (Area × Intensity) ¹	0.6	0.4	>99.9%	>99.9%	>99.9%
Comparison with Reference Dentifrice in change from baseline in mean Total MLSI (Area × Intensity) ¹	0.3	0.4	99.8%	99.7%	99.8%
Within change from baseline in the mean VITA shade score ²	2	2	>99.9%	>99.9%	>99.9%
Comparison with Reference Dentifrice in change from baseline in the mean VITA shade score ²	1	2	91.5%	86.1%	90.2%

1) Estimates of mean difference and SD were based on results from a previous GSKCH study of similar design [CCI](#)

2) Estimates of mean difference and SD were based on results from previous GSKCH studies of similar design [CCI](#). Within treatment study reductions in the mean VITA shade score are expected to be greater in this study due to greater baseline VITA shade scores and an 8 week primary assessment instead of 4 weeks. As such, the SD is also assumed to increase, so an effect size (mean difference/SD) of 0.5 is assumed.

3) Based on carrying out a two tailed one-sample (within Experimental Dentifrice) or two-sample (Comparison with Reference Dentifrice) t-test at the 5% significance level using PASS software version 19.0.1.

4) Simulation using SAS9.4 software based on stated assumptions for all endpoints and graphical approach analysis as described in [Figure 4-1](#)

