4.4.2.2.1 Statistical Hypothesis, Model and Method of Analysis

The following null and alternative hypotheses will be evaluated:

- H_0 : There is no treatment difference
- H_1 : There is a treatment difference

The following study product comparisons will be analyzed:

- Experimental Dentifrice 1 versus Reference Dentifrice at week 8
- Experimental Dentifrice 2 versus Reference Dentifrice at week 8

The results for this endpoint will be obtained from the MMRM detailed in [Section 4.4.1.1](#). Mean differences between each Experimental Dentifrice compared to the Reference Dentifrice in the change from baseline in mean Total MLSI (A×I) score at week 8 will be presented along with 95% CIs and adjusted p-values (following the graphical approach in [Figure 4-1](#)) in Table 14.2.2.2.1. Significance testing will be conducted at the two-sided 5% significance level.

The assumption of normality and homogeneity of variance in the MMRM will be investigated. In case of violation of these assumptions, a suitable nonparametric test (the Van Elteren test, adjusted for the randomization stratification) will be performed for each comparison at week 8 and results will be provided to support the MMRM results.

4.4.2.3 Secondary Efficacy Endpoint 3

The Secondary Efficacy Endpoint 3 will be the change from baseline in mean VITA shade score at week 8 and the comparison of each Experimental Dentifrice to the Reference Dentifrice.

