4.4.2.3.1 Statistical Hypothesis, Model and Method of Analysis

The following null and alternative hypotheses will be evaluated:

- H_0 : There is no treatment difference

- H_1 : There is a treatment difference

The following study product comparisons will be analyzed:

- Experimental Dentifrice 1 versus Reference Dentifrice at week 8
- Experimental Dentifrice 2 versus Reference Dentifrice at week 8

The results for this endpoint will be obtained from the MMRM detailed in [Section 4.4.2.1.1](#). Mean differences between each Experimental Dentifrice compared to the Reference Dentifrice in the change from baseline in mean VITA shade score at week 8 will be presented along with 95% CIs and adjusted p-values (following the graphical approach in [Figure 4-1](#)) in Table 14.2.3.2.1. Significance testing will be conducted at the two-sided 5% significance level.

The assumption of normality and homogeneity of variance in the MMRM will be investigated. In case of violation of these assumptions, a suitable nonparametric test (the Van Elteren test, adjusted for the randomization stratification) will be performed for each comparison at week 8 and results will be provided to support the MMRM results.

4.4.2.4 Secondary Efficacy Endpoint 4

The Secondary Efficacy Endpoint 4 will be the change from baseline in mean Total MLSI (A×I) score at week 4 for each study product and the comparison of each Experimental Dentifrice to the Reference Dentifrice.

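### The SAP names Van Elteren, a test for independent groups, as the non-parametric check on paired within-product hypotheses, including the primary one

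*SAP*

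**What the plan says.** SAP 4.4.1.2 (primary endpoint, mean Total MLSI) sets the null hypothesis as no difference between baseline and week 8. It lists two comparisons, one per experimental dentifrice; the first reads "For Experimental Dentifrice 1, baseline versus week 8". The main analysis is an MMRM. If normality or homogeneity of variance fails, "a suitable nonparametric test (the Van Elteren test, adjusted for the randomization stratification) will be performed for each comparison at week 8", and the result supports the MMRM.

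SAP 4.4.2.1.1 repeats this for VITA shade, again listing only within-product comparisons. SAP 4.4.2.6.1 (site scores), 4.4.2.7.1 (area and intensity) and 4.4.3.1.1 (EasyShade co-ordinates) use the same sentence for weeks 4 and 8. Their results cover both within-product and between-product tests.

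Comparisons with Reference have their own sections, each with the same Van Elteren sentence: SAP 4.4.2.2.1 for MLSI ("Experimental Dentifrice 1 versus Reference Dentifrice at week 8") and SAP 4.4.2.3.1 for VITA (such as "Experimental Dentifrice 2 versus Reference Dentifrice at week 8").

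Protocol 12.3.1 asks only for a suitable non-parametric test adjusted for the randomization strata and names none. The choice of test therefore enters with the SAP.

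**The concern.** Van Elteren combines rank-sum comparisons of two independent groups across strata. A change from baseline within one product is a one-sample, or paired, question. The plan draws this line itself in its power calculation: SAP 1.4, footnote 3, relies on a "two tailed one-sample (within Experimental Dentifrice) or two-sample (Comparison with Reference Dentifrice) t-test".

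The within-product hypothesis carries the study. Protocol section 3 states: "This study will be considered successful if either of the experimental dentifrices demonstrates statistically significant stain removal". As written, that hypothesis has no usable non-parametric check. If the fallback is triggered, the programmer must either improvise a test or run one that answers a different question.

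The within-product and between-product answers can realistically diverge. In Protocol 2.2, an earlier 8-week MLSI study found a significant reduction from baseline, yet "no statistically significant differences were observed between the test products and a regular fluoride dentifrice". An earlier 4-week shade study found a significant improvement from baseline for the alumina/STP dentifrice, yet "there was no statistically significant difference between any of the test products and the regular fluoride dentifrice".

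**Working it through.** **1. Hypothesis against test, by section**

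| SAP section | Comparison | Van Elteren fits? |
|---|---|---|
| 4.4.1.2 | within-product only, MLSI | no |
| 4.4.2.1.1 | within-product only, VITA | no |
| 4.4.2.2.1 and 4.4.2.3.1 | Experimental versus Reference | yes |
| 4.4.2.6.1, 4.4.2.7.1 and 4.4.3.1.1 | both kinds | only for the between-product part |

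**2. The plan's own power figures** (SAP 1.4, n = 90 per arm, noncentral t)

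- Within-product, noncentrality = (mean/SD)·√90. MLSI: (0.6/0.4)·√90 = 14.2. VITA: (2/2)·√90 = 9.5. Power exceeds 99.9% in both, as stated.
- Versus Reference, noncentrality = (difference/SD)·√(90/2). MLSI: 0.75·√45 = 5.03, power 99.88% at 5% and 99.71% at 2.5% (stated 99.8% and 99.7%). VITA: 0.5·√45 = 3.35, power 91.56% and 86.19% (stated 91.5% and 86.1%).

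These reproduce, using a one-sample test within a product and a two-sample test against Reference.

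**3. Van Elteren on one product's change scores**

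In a stratum with groups of n and m, and N = n + m, the statistic adds w·[W − n(N+1)/2] with w = 1/(N+1). Without ties the variance of W is n·m·(N+1)/12. With a single group m = 0, so W equals its expectation and the variance is zero. The ratio is 0/0 and no p-value exists.

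**4. If programmed on change scores against Reference**

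Monte Carlo, normal scores, 90 per arm, four strata, two-sided 5%. The Experimental arm is at its planned change. Ranges are over separate simulation runs of 3000 or 5000 trials per case where the number of trials is recorded.

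| Endpoint | True difference from Reference | Van Elteren rejects | Signed-rank within Experimental rejects |
|---|---|---|---|
| MLSI (0.6, SD 0.4) | 0 | 4.7–5.5% | 100% |
| | 0.1 (assumed) | 36–37% | 100% |
| | 0.3 (planned) | 99.6–99.9% | 100% |
| VITA (2, SD 2) | 0 | 4.9–5.4% | 100% |
| | 0.5 (assumed) | 35–37% | 100% |
| | 1 (planned) | 89–90% | 100% |

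**5. If baseline and week 8 are treated as independent groups**

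Rejection rate with no true change, nominal 5%. The documents give no baseline-to-week-8 correlation, so a range is assumed.

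| Correlation | Strata unrelated to score | Strata split at baseline median |
|---|---|---|
| 0.5 | 0.6–0.8% | 3.1–3.6% |
| 0.7 | about 0.1% | 1.2–1.8% |
| 0.8 | at most 0.03% | 0.6–0.7% |

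The signed-rank test gives 4.8–5.5%. For MLSI the right-hand column is closer to the trial, because the strata include baseline Total MLSI (SAP 3.2).

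**6. Does the replacement hold its level?**

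No true change, the same correlations, smoking split 50/50 and baseline cut at the median or 70th percentile (all assumed), 6000 runs per case:

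- unstratified signed-rank: 4.6–5.4%
- four strata weighted by 1/(stratum size + 1): 3.7–5.0%
- four strata, unweighted sum: 6.4–18.8%

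The signed-rank sum grows roughly with the square of stratum size. An unweighted sum therefore lets the larger baseline stratum dominate, and its drift back towards the mean is not offset.

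Entry thresholds (Protocol 5.2, items 5e and 5f) also cause regression to the mean. The documents do not say what fraction they exclude. If they remove the lowest 5/10/20% of baselines (assumed), rejection with no true change is 5.9–7.7 / 8.3–15.1 / 17.4–39.0% for the unstratified signed-rank test. It is 5.3–6.4 / 7.3–11.0 / 15.6–32.4% for the weighted version, and 6.0–8.6 / 8.8–16.2 / 18.7–41.7% for a one-sample t-test standing in for the MMRM within-product test. This affects all the within-product tests examined, and the replacement does not remove it.

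**The case against.** The strongest case is that almost nothing depends on this. The test runs only if MMRM assumptions fail, only supports the MMRM, and sits outside the graphical procedure. The planned within-product effects are 1.5 SD (0.6/0.4) and 1.0 SD (2/2) at n = 90. Even the misuse in step 5 rejected in 100% of 2000 runs in each of 12 cases at those effects, so it costs no power there and produces no excess false positives. The SAP also tabulates the median, minimum and maximum change by product, so gross skew would be visible. All of this stands, and it sets the severity.

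Three narrower objections stand in part:

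- The error is explicit in two sections. In the other three, the phrase about each comparison could be read as Experimental versus Reference only. Those sections do report within-product tests, though, so they need at least a clarification.
- Only one of the two earlier studies is an 8-week MLSI precedent; the other is a 4-week shade study.
- Step 4 shows no malfunction of Van Elteren. Rejecting 5% when products are equal is correct behaviour. The table shows only that it answers a different question.

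Two defences fail. Calling the test suitable left room in the Protocol, but the SAP closed it by naming one test. Reading the sentence as meaning versus Reference duplicates SAP 4.4.2.2.1 and 4.4.2.3.1 and leaves the primary hypothesis with no non-parametric check.

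**Conclusion.** The point holds as a minor SAP correction. For the within-product hypotheses the named test is wrong as written: it either cannot be computed, tests a different hypothesis, or ignores the pairing and becomes conservative. That conclusion follows from the structure of the test and needs no assumption.

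The sizes in steps 4 to 6 are illustrations, since the SAP specifies neither way of applying the test. They rest on normal scores, 90 per arm, and assumed correlations, stratum splits and smaller differences. No planned sample size, power or alpha changes, and at the planned effects the study's conclusion would not change.

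**What to change.** In SAP 4.4.1.2, 4.4.2.1.1, 4.4.2.6.1, 4.4.2.7.1 and 4.4.3.1.1, name a Wilcoxon signed-rank test on change from baseline for within-product comparisons. Keep Van Elteren on change scores for Experimental versus Reference. Choose one form before unblinding:

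- **Unstratified**, recording in SAP section 5 the departure from the stratification adjustment in Protocol 12.3.1; or
- **Stratified** over the four randomization strata with weights 1/(stratum size + 1), which keeps the Protocol wording. Do not use an unweighted sum.

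A sign test may be named for clearly skewed changes. Do not apply the within-product rank test to ΔE*, which cannot be negative. Add a note that the signed-rank test, like the MMRM within-product test, does not remove regression to the mean from enrolling on high baseline stain and shade.

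The cost is one clause in each of five sections, the regression-to-the-mean note, one line in SAP section 5 if the unstratified form is chosen, and a small programming change. Data collection, sample size, alpha and the MMRM are untouched.

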4.4.1.3 Supportive Analyses

A PP analysis will be performed on the change from baseline in the mean Total MLSI (A×I) score if there is more than 10% difference in the number of subjects between the PP and mITT populations. A decision on whether a PP analysis will be performed will be made prior to study unblinding (release of the randomization codes).

A summary of the mean Total MLSI (A×I) will be presented for the PP Population in Table 14.2.2.1.2. Statistical analysis of the mean Total MLSI score will be presented for the PP population in Table 14.2.2.2. In addition, the mean profiles of the mean Total MLSI (A×I) (Figure 14.2.1.2) at each time point will be plotted by study product for all subjects in the PP Population.

4.4.2 Secondary Efficacy Endpoints

4.4.2.1 Secondary Efficacy Endpoint 1

The Secondary Efficacy Endpoint 1 will be the change from baseline in the mean VITA shade score at week 8 within each study product.

Tooth shade (color) of the facial surfaces of the four central and lateral maxillary incisors (tooth numbers 7-10) will be assessed by a single, trained clinical examiner using the VITA Bleachedguide 3D-MASTER. The VITA Bleachedguide 3D-MASTER uses a value-ranked

ordered scale from 1 (the lightest) to 29 (the darkest). The shade level of each tooth surface is scored visually by the clinical examiner with reference to the Bleachedguide.

The mean VITA shade score for each subject at each visit is calculated as the mean VITA shade score over all non-missing facial surfaces of the four central and lateral maxillary incisors.

Descriptive statistics (n, mean, SD, Standard Error [SE], median, minimum, and maximum) will be presented for the mean VITA shade score at each assessment time point (absolute and change from baseline) in Table 14.2.3.1.1 for all subjects in mITT Population by study product. Raw means (\pm SE) of mean VITA shade scores at each time point will be plotted by study product in Figure 14.2.2.1 respectively for all subjects in mITT population.

